In an innovative use of an established and well validated intervention for insomnia, we propose to examine the direct effects of sleep on biomarkers of CVD risk outcomes among persons with PTSD and comorbid insomnia disorder (ID; see Figure 1). In this 2-arm RCT, 150 participants with PTSD and ID will be randomized at a 2:1 ratio to either CBT-I, or a minimal contact control condition (CCC). We anticipate that we may need to consent and screen as many as 500 participants to reach this goal. Sleep efficiency as measured by actigraphy will be the primary sleep outcome measure. Other parameters [total sleep time (TST) wake after sleep onset (WASO), sleep fragmentation] will be measured with a multi-modal assessment strategy including validated self-report measures, sleep diaries collected *via* Qualtrics, and objective sleep measurement (i.e., actigraphy). Sleep diaries and actigraphy will be continuously collected for 10-weeks (including a week-long baseline, 8-week period for CBT-I or CCC, and one-week post treatment) and for a week-long period at the 6-month follow-up. The primary outcomes for this clinical trial are established biomarkers of CVD risk, including flow mediated dilation, SNS activity, nighttime BP, nighttime BP dipping, and ASCVD risk. These biomarkers will be assessed at three time points: baseline, post-intervention (8-weeks), and 6-month follow-up. The 6-month follow-up period will allow us to evaluate whether the intervention effects on CVD risk are sustained beyond the immediate post-intervention period. Timing for the 6-month follow-up visit will be 6 months after

the baseline assessment or three months after the post-intervention assessment, whichever is later. Participants in both arms will continue with usual medical care.

C.2. Recruitment

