The study is designed as a two-arm trial to examine the effects of CBT-I on objective sleep parameters and CVD risk biomarkers. Statistical analyses will be performed using SAS, version 9.4 (SAS Institute, Cary, NC) and Mplus, version 7 (Muthén & Muthén, 2012). The first step in the analysis will be to calculate descriptive statistics, including graphical displays, to summarize all study variables. We will construct individual and mean trajectory plots of the longitudinal outcome variables to understand their general trends from baseline to post-intervention and 6-month follow-up. In addition, we will explore the variability and correlation structure of the longitudinal outcome variables. We will stratify by trauma exposure (combat or non-combat) and objectively measured sleep duration (<6 hours or \geq 6 hours).

Each of the study hypotheses will be examined using data collected at baseline, immediately following the 8-week intervention phase (i.e., post-intervention), and again at 6-month follow-up. Given nesting of these multiple observations within each participant, multilevel modeling (MLM) will be used to examine each set of hypotheses. MLM is a technique for analyzing repeated observations of data across multiple individuals (Searle, Casella, & McCulloch, 1992). Unlike repeated-measures ANOVA,

MLM uses all available data and can handle data missing at random. MLM can also accommodate imbalanced data and unequal variances.

To manage the problem of random positive findings when making multiple comparisons within each hypothesis (i.e., random significant findings occurring due to multiple proposed analyses), we will correct alpha using the “false discovery rate approach” described by Glickman (Glickman, Rao, & Schultz, 2014). This methodology differentiates random findings from hypothesis-driven outcomes and is more powerful than Bonferroni-type alpha adjustments that control the false-positive rate (Benjamini, 2010; Glickman, Rao, & Schultz, 2014; Schafer & Olsen, 1988; Searle, Casella, & McCulloch, 1992; Simes, 1986). Specifically, alpha correction will be applied to Aims 1 and 2 but not to the Supplemental Aim, given that any exploratory hypothesis that is supported would require validation with further research.

D.2. Missing Data Considerations

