MLM can accommodate data missing at random, using maximum likelihood-derived estimates based on all available data. That said, data may be missing not at random (MNAR). That is, the outcome data may be systematically missing, for instance, from participants who experience no benefit from CBT-I. Nevertheless, even in the case of MNAR data, estimates derived from analyses examining Hypothesis 2 (addressing the within-person associations of change in insomnia with change in CVD risk) and the Supplemental Aim are unlikely to be affected by data missingness. After all, even if participants who benefit the least from CBT-I drop out of the study, we still anticipate observing the same magnitude of association between improved sleep and changes in cardiovascular biomarkers and QoL. By contrast, Hypothesis 1, which examines clinical response to CBT-I, would be affected by MNAR data. As such, we will conduct sensitivity analysis on three missing data approaches for Aim 1. First, we will conduct a completer analysis, analyzing only data from participants who complete each of the three assessments. Second, we will allow the maximum-likelihood estimation to generate estimates for all available data. In a third approach, we will use an intent-to-treat approach, assuming that missing post-intervention and/or 6-month follow-up data are evidence of stagnation. Specifically, we will use last observation carried forward in the cases of missing data.

D.3. Primary and Secondary Analyses

To examine the degree to which CBT-I is associated with improved sleep efficiency and insomnia severity index score (manipulation check), linear MLM will be used to model sleep outcomes as a function of treatment (CBT-I, control), time (baseline, post-intervention, 6-month follow-up), and the interaction between treatment and time. Planned treatment contrasts in change from baseline to post-intervention and 6-month follow-up will be examined within the context of the model. To determine the degree to which CBT-I is associated with improved CVD risk biomarkers (Hypotheses 1a), each of the 6 CVD risk variables (24-hr SBP, nighttime SBP dipping, FMD, 24-hr epinephrine, and norepinephrine) will also be modeled as a function of treatment, time, and their interaction, with planned treatment contrasts in change from baseline at post-intervention and 6-month follow-up. Dichotomized 10-year ASCVD risk scores (Hypothesis 1b) and QoL scores (Hypothesis 1c) will similarly be modeled via logistic MLM.

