Calculations are based on Aims 1 and 2. Because each of the analyses will make use of repeated-measures data, statistical power will depend on the effective sample size (ESS). For Hypotheses 1, which will examine treatment effects associated with differences in sleep and cardiovascular outcomes, the ESS will be equivalent to the total number of observations (number of participants \times number of data collections) adjusted for intra-individual correlations. As the intra-individual, or intra-class, correlation (ICC) decreases, the ESS increases. Given that we anticipate substantial intra-individual variability on account of the intervention, an ICC of .50, representing an equal allotment of variance attributable to inter-individual differences and intra-individual variability, provides a conservative estimate of the ESS. With a sample of 150 contributing 3-time points of data each and an ICC of .50, the ESS would be 225. Even with 10% attrition post-intervention and then again at the 6-month follow-up, the ESS would be 215. Assuming equivalent attrition rates among the 100 CBT-I participants and 50 controls, this would have 80% power to detect treatment effects equivalent to Cohen's d of 0.41 via a two-tailed test with an alpha of .05. For reference, a meta-analysis on CBT-I (Okajima, Komada, & Inoue, 2011) found 12-month treatment effects on SOL, WASO, and sleep efficiency equivalent to $d = 0.45, 0.47$, and 0.54 , respectively. *Six-month follow-up CBT-I treatment effects in Talbot et al.'s (2014) RCT of CBT-I in persons with PTSD far exceeded these for SE ($d = 1.48$), SOL ($d = 1.31$), and TST ($d = 0.76$).* Moreover, Talbot et al. (2014) recorded large effects of CBT-I on 6-month increases in psychosocial functioning ($d = 1.02$). Although the specific impact of CBT-I on CVD risk remains untested, comparable behavioral-health interventions, such as stress management, have shown robust effects. For instance, in one study, 16 weeks of weekly 1.5-hour stress-management training compared to usual care was sufficient to achieve large increases in FMD ($d = 2.32$; Blumenthal,

[name] et al., 2005). In another study, a similar regimen of weekly group stress-management sessions was associated with significantly reduced time to adverse cardiac events, $HR = 0.26$ (95% CI: 0.07-0.90), in comparison to usual care. Given these effect sizes, the present study should have adequate power to detect treatment effects similar to those found in previous trials.

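### The 80% power claimed at d = 0.41 for Hypothesis 1 does not apply to the planned change-from-baseline contrasts, which have about 60% power

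*Combined protocol and SAP*

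**What the plan says.** D.4 defines the ESS for Hypothesis 1 as participants times data collections, adjusted for within-person correlation. It then states: "With a sample of 150 contributing 3-time points of data each and an ICC of .50, the ESS would be 225". After 10% attrition at post-intervention and again at 6 months it gives an ESS of 215. For equal attrition rates "among the 100 CBT-I participants and 50 controls", it says "this would have 80% power to detect treatment effects equivalent to" Cohen's "d of 0.41 via a two-tailed test with an alpha of .05".

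D.4 calls an ICC of .50 conservative because "As the intra-individual, or intra-class, correlation (ICC) decreases, the ESS increases".

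C.1 lists the three biomarker assessments as baseline, post-intervention and 6-month follow-up; C.6.1 places the baseline ambulatory BP assessment before randomisation.

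D.3 models each CVD variable on treatment, time and their interaction, "with planned treatment contrasts in change from baseline at post-intervention and 6-month follow-up". The sleep outcomes get the same contrasts. D.1 adds that "alpha correction will be applied to Aims 1 and 2 but not to the Supplemental Aim".

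**The concern.** D.4 and D.3 describe different tests. The ESS calculation suits a comparison of arm means over all three visits with the full effect present at each, baseline included. The planned contrasts subtract the baseline arm difference, so the baseline visit adds noise to the estimate and carries no treatment effect. Nowhere does the plan give power for those contrasts.

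The direction of the ICC argument is also at issue. A lower ICC raises the ESS, but it makes a change score noisier.

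At stake is how a null result is read. D.4 implies a 20% chance of missing an effect of d = 0.41. If the chance is nearer 40% for each contrast, a non-significant biomarker result is much weaker evidence against an effect of that size than D.4 suggests.

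**Working it through.** **Inputs.** N = 150, 100 v 50 (C.1, D.4); three visits including baseline (C.1); ICC .50, attrition 10% then 10%, d = 0.41, two-sided alpha .05 (D.4); contrasts in change from baseline (D.3). Attrition leaves 135 at post-intervention and 121.5 at 6 months.

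**1. The plan's own figure.** A participant with m visits contributes m/(1 + (m − 1)·ICC).
- No attrition: 450/(1 + 2 × .5) = 225.
- With attrition, 121.5 have three visits, 13.5 have two and 15 have one: 121.5 × 1.5 + 13.5 × 1.333 + 15 × 1 = 215.25.
- Split 2:1, SE = √(1/143.3 + 1/71.7) = 0.1447. Detectable d = 2.80 × 0.1447 = 0.405, and power at d = 0.41 is 81%.

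So 225, 215 and 0.41 all reproduce. The arithmetic is right for the test it assumes.

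**2. The planned contrast, simple form.** With d in outcome-SD units, the variance of the arm difference in change is 2(1 − ICC)(1/n₁ + 1/n₂). At ICC .50 the first factor is 1, and with a 2:1 split 1/n₁ + 1/n₂ = 4.5/N.
- Post-intervention: SE = √(4.5/135) = 0.183; detectable d = 0.51; power at 0.41 = 61%.
- 6 months: SE = √(4.5/121.5) = 0.192; detectable d = 0.54; power at 0.41 = 57%.
- No attrition: SE = √(4.5/150) = 0.173; detectable d = 0.49; power 66%.

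**3. The planned model, all available data.** This uses the maximum-likelihood information matrix for treatment by time under compound symmetry, with 81%, 9% and 10% of participants having three, two and one visits.

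| ICC | Detectable d, post / 6 months | Power at 0.41, post / 6 months |
|---|---|---|
| .30 | 0.60 / 0.62 | 49% / 46% |
| .50 | 0.51 / 0.52 | 62% / 59% |
| .60 | 0.45 / 0.47 | 72% / 69% |
| .70 | 0.39 / 0.41 | 83% / 80% |

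Power rises with the ICC, the reverse of D.4's argument.

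**4. Other attrition.** With the 142 shown at both later assessments in Table 3 (section E), detectable d is 0.495 and power is 64%.

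**5. Average over all three visits.** If this were meant, an effect of 0.41 at the two later visits averages 0.41 × 2/3 = 0.273. With SE 0.145, power is 47%.

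**6. Multiplicity, illustrative worst case.** D.3 refers to six CVD variables. If only one responds and must pass .05/6 (critical value 2.638), power at d = 0.41 and ICC .50 is 36% / 33%. Detectable d is (2.638 + 0.842) × 0.180 = 0.63 at post-intervention and 3.480 × 0.187 = 0.65 at 6 months.

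**The case against.** Several points can fairly be made for the plan.

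- *No sum is wrong.* True. The fault is a mismatch between formula and test, but the stated power still does not belong to the test that will be run.
- *D.4 does not say which SD standardises d.* Also true. In change-score SD units the ICC sweep disappears and the simple contrast gives 61% / 57% at any ICC. That does not restore 80%. The ESS calculation itself works in outcome-SD units, and there the ICC argument is reversed.
- *About 60% is a per-visit figure, and D.3 does not name one visit as decisive.* At ICC .50, unadjusted, with d = 0.41 at both visits, the 2-df interaction test has 64%, the average of the two contrasts 74%, and at least one significant contrast 77%. None reaches 80%, and neither the average nor the at-least-one rule is in the plan.
- *A model constraining the baseline means to be equal would do better.* It gives 74% / 70% per visit and 88% for the average of the two later visits. The plan specifies neither.
- *The benchmark effects in D.4 are mostly larger.* At the cited sleep-efficiency effect of 0.54, power is 85% / 82%. That is reassuring for the manipulation check. For the CVD outcomes, D.4 itself says that the specific effect of CBT-I is untested.
- *The .05/6 threshold is a choice.* This stands: D.3 says six variables but lists five, D.1 does not fix the size of the FDR family, and the loss is smaller if several outcomes respond. The 36% / 33% figures mark a lower end only.

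**Conclusion.** The concern holds. The 80% at d = 0.41 belongs to a comparison that D.3 does not plan and that credits a pre-treatment visit with a treatment effect. For the planned linear-model contrasts, power is 62% at post-intervention and 59% at 6 months, with detectable d of 0.51 and 0.52. These figures rest on the plan's ICC, allocation and attrition, unadjusted two-sided alpha of .05, compound symmetry, and d in outcome-SD units. The stated figure would be reached at an ICC of about .70. D.4 gives no support for a value that high and expects substantial within-person variability, which points the other way. The FDR correction lowers power by an amount that depends on the family and on how many outcomes respond. The calculation does not cover Hypotheses 1b and 1c, which D.3 assigns to logistic models.

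**What to change.** In D.4, replace the ESS calculation for Hypothesis 1 with power for the contrasts in D.3:

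- State that, at ICC .50, 2:1 allocation, 10% then 10% attrition and unadjusted two-sided alpha of .05, the trial has 80% power for d = 0.51 at post-intervention and 0.52 at 6 months, with d in units of the outcome SD.
- Give the range for ICC .30 to .70: 0.60 down to 0.39 at post-intervention, and 0.62 down to 0.41 at 6 months.
- Define the FDR family and give the detectable effect after correction. With six outcomes and a single responder, it is about 0.63 and 0.65.
- Delete the statement that ICC .50 is conservative because a lower ICC helps.
- Say that these figures apply to the linear models only.

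The cost is SAP wording and a less favourable detectable effect. No extra participants are needed, and the analysis in D.3 is unchanged.

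If the sponsor wants to keep a detectable effect near 0.41, it could instead prespecify a baseline-constrained average over the two later visits (88% power at ICC .50, unadjusted). That changes the Hypothesis 1 test and would have to be fixed before outcome data by arm are seen.

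### D.4's 80% power for Aim 1 belongs to a single uncorrected .05 test, not to the FDR-corrected tests that D.1 plans

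*Combined protocol and SAP*

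**What the plan says.** Section D.1 plans to control chance findings among the comparisons inside each hypothesis by a false discovery rate approach, and specifies that "alpha correction will be applied to Aims 1 and 2 but not to the Supplemental Aim". It does not give q, and it does not count the tests in any family.

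Section D.3 models each Hypothesis 1a biomarker by treatment, time and their interaction. It plans treatment contrasts in change from baseline at two visits, post-intervention and 6 months. It refers to six variables but lists five.

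Section D.4 says its calculations rest on Aims 1 and 2. For Hypothesis 1: "With a sample of 150 contributing 3-time points of data each and an ICC of .50, the ESS would be 225". After "10% attrition post-intervention and then again at the 6-month follow-up, the ESS would be 215". With "100 CBT-I participants and 50 controls", it concludes that "this would have 80% power to detect treatment effects" of d "of 0.41 via a two-tailed test with an alpha of .05". For Aim 2 it gives an effective sample size (ESS) of 256 and 80% power for a standardised coefficient of .15, with no alpha. D.4 does not mention the FDR correction, a number of tests or a reduced threshold.

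**The concern.** A power figure is useful only if it refers to the rule by which a result will be declared. D.1 says an Aim 1 biomarker result counts after FDR correction across its family. D.4 gives the chance that one test, taken alone, reaches p ≤ .05. These are different events.

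With Benjamini-Hochberg at q = .05, every rejected test also has p ≤ .05, so corrected power cannot exceed the uncorrected figure. How far it falls depends on how many outcomes truly respond. D.4 itself acknowledges that the effect of CBT-I on cardiovascular risk has not been tested, so the plan cannot take for granted that most biomarkers will move. If only one or two do, someone interpreting a non-significant biomarker result would be relying on 80% when the planned procedure had less.

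**Working it through.** **Inputs.** From D.4: d = 0.41, two-sided alpha .05, 150 participants split 2:1, three visits, ICC .50, and 10% attrition twice. From D.3: five listed outcomes (six stated) and two contrasts each. The family is therefore 5-6 tests with one test per outcome, or 10-12 if both contrasts count. Assumed, because the plan does not state them: Benjamini-Hochberg, q = .05 (with .10 as the alternative), and independent tests.

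**Step 1: reproduce the ESS.** A participant with k visits contributes k / (1 + (k − 1) × 0.5).
- No attrition: 450 / 2 = 225, as stated.
- With attrition: 121.5 participants with three visits, 13.5 with two and 15 with one. 121.5 × 1.5 + 13.5 × 1.333 + 15 × 1 = 215.25, as stated.

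**Step 2: reproduce the power.** Split 215 as 143.3 and 71.7. √(143.3 × 71.7 / 215) = 6.91, and the expected z is 0.41 × 6.91 = 2.83. At two-sided .05, power = Φ(2.83 − 1.96) = 80.9% (80.5% by noncentral t). One-sided .05 gives 88.3%, which does not match. The stated 80% is thus the uncorrected two-sided figure, with no allowance for multiplicity.

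**Step 3: strictest FDR step, alpha = .05/m.** Power = Φ(2.83 − z), where z is the two-sided critical value. The d detectable with 80% power is (z + 0.842) / 6.91.

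| m | z | Power at d = 0.41 | d for 80% | ESS for 80% at d = 0.41 |
|---|---|---|---|---|
| 5 | 2.576 | 60.2% | 0.49 | 315 |
| 6 | 2.638 | 57.8% | 0.50 | 327 |
| 10 | 2.807 | 51.1% | 0.53 | 357 |
| 12 | 2.865 | 48.8% | 0.54 | 369 |

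**Step 4: Benjamini-Hochberg by simulation.** At least 100,000 replicates; independent tests; every true effect has expected z = 2.83. Entries are average power per true effect.

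| q | m | One true effect | About half true | All true |
|---|---|---|---|---|
| .05 | 5 | 61% | 67% (2 of 5) | 78% |
| .05 | 6 | 59% | 69% (3 of 6) | 78% |
| .05 | 10 | 52% | 68% (5 of 10) | 78% |
| .05 | 12 | 50% | 68% (6 of 12) | 78% |
| .10 | 5 | 71% | 77% | 87% |
| .10 | 6 | 69% | 79% | 87% |
| .10 | 10 | 62% | 79% | 87% |
| .10 | 12 | 59% | 79% | 87% |

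A correlation of .5 among the tests at q = .05 lowers these slightly: about 49-61% with one true effect and 75-77% with all true.

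The rows for 10 and 12 tests credit each visit contrast with the full ESS of 215. D.4 builds that ESS by pooling all three visits, whereas a change-from-baseline contrast uses two. Those rows are therefore conditional on that credit. The rows for 5 and 6 tests fit D.4's own construction better.

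**Step 5: Aim 2.** ESS = 150 × 0.9 + 150 × 0.81 = 256.5, as stated. Treating the coefficient of .15 as a correlation, the expected z is atanh(.15) × √253 = 0.1511 × 15.91 = 2.404.
- Uncorrected two-sided .05: Φ(2.404 − 1.960) = 67%. The coefficient detectable with 80% power is about .174.
- Uncorrected one-sided .05: 77.6%.
- Two-sided .05/5: Φ(2.404 − 2.576) = 43%. Two-sided .05/6: Φ(2.404 − 2.638) = 41%.

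**The case against.** Four arguments can be made for leaving D.4 as it is.

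1. *FDR control is mild when many outcomes respond.* This is correct. If all respond at q = .05 with independent tests, power is 78%, close to the stated figure. At q = .10 it is 87%, above it, because that procedure can then reject at p-values over .05. The shortfall is a range, and one end of it is small.

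2. *The corrected figures rest on inputs the plan does not give.* Also correct: q, the family size and the correlation are all assumptions here. This limits how firmly the size can be put, but it does not remove the mismatch. The missing q and family are themselves what needs stating.

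3. *The effects D.4 cites are larger than 0.41.* Its only benchmark on a Hypothesis 1a outcome is an FMD effect of d = 2.32, which clears any threshold above, but it comes from stress management. The cited meta-analytic CBT-I effects of 0.45, 0.47 and 0.54 are for sleep, which the plan treats as a manipulation check. They do not establish what CBT-I will do to the biomarkers.

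4. *Average power per effect is only one metric.* With two true effects among 5-6 independent tests at q = .05, the chance of declaring at least one is about 83-85%. That stands for that question, but it is not what D.4 reports.

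Two stronger readings are tempting. A reader might infer that the planned tests have about 50% power. The documents do not support this as a single figure: it needs q = .05, 10-12 tests, one true contrast, and the pooled ESS credited to each visit contrast. A reader might also infer that Aim 2 shows the same conflict of alphas. It does not, because its paragraph states no alpha to conflict with D.1. Its difficulty comes earlier: at uncorrected two-sided .05 its 80% is already not reached.

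**Conclusion.** The mismatch is real and can be read directly from D.1 and D.4. The Aim 1 power is that of a lone uncorrected two-sided .05 test (80.9% on recalculation), while Hypothesis 1a will be judged after FDR correction.

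The size depends on what the plan leaves open. With D.4's ESS accepted, Benjamini-Hochberg at q = .05 and independent tests, the loss from 81% is about 20-22 points for a lone effect among 5-6 tests, about 29-31 points among 10-12, and about 3 points if every effect is real. At q = .10 a lone effect still falls short, while power exceeds the stated value if all respond.

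This is a fault in the power statement. It does not make the decision rule or the sample size invalid, and it does not show that the trial is underpowered for the effects it will meet. The ESS method was taken as given and is not assessed here.

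**What to change.** In D.1, state q and list the tests in the family for each hypothesis: whether both visit contrasts count, and whether Hypothesis 1a has five or six outcomes.

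Then restate D.4's Aim 1 figure in one of two ways:
- label the 80% at d = 0.41 as power before FDR correction, and add the corrected range with its assumptions (q, number of tests, number of true effects, correlation); or
- give the d detectable with 80% power at the corrected threshold.

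No fixed pair of corrected percentages should go into the SAP until q and the family are settled, because the values move with both.

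For Aim 2, state the alpha and sidedness and recompute, first without correction and then under the FDR rule.

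The cost is wording only, with no change to recruitment, treatment or data collection. The stated power is likely to become less favourable.

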To examine whether increased sleep efficiency is associated with decreased CVD risk (Hypothesis 2), lagged values will be used to create changes scores, defined by subtracting values for sleep efficiency and each of the CVD risk parameters measured at time $t-1$ from those measured at time t . Thus, decreases will be reflected by negative change scores and increases by positive change scores. Linear MLM will then be used to model each of the change scores corresponding to the 6 aforementioned CVD risk variables using the general equation below:

$$\text{CVD risk}_{\Delta t} = B0 + B1 * \text{Sleep efficiency}_{\Delta t} + B2 * \text{CVD risk}_{t-1} + B3 * \text{Sleep efficiency}_{t-1}$$

where change in the CVD risk outcome from $t-1$ to t will be modeled as a function of corresponding change in sleep efficiency, covarying for sleep efficiency measured at $t-1$ and the outcome in question measured at $t-1$. To explore the heterogeneity of CBT-I treatment response on sleep (Supplemental Aim), potential moderators (trauma type, insomnia phenotype, medication use, biological sex, and minority status) of the effect of CBT-I treatment on sleep outcomes will be examined via interaction effects. Specifically, sleep efficiency and sleep quality measured at baseline, post-intervention, and 6-month follow-up will be modeled in separate analyses as a function of treatment, time, a given moderator, and their second- and third-order interactions. To avoid the effects of multicollinearity, each moderator will be tested in a separate analysis. To determine whether the effect of changes in sleep efficiency on changes in CVD risk parameters vary by each of the aforementioned moderators, the analyses specified above for Hypothesis 2 will be modified to examine the main effect of a given moderator as well as the interaction effect of the moderator and sleep efficiency on each of the CVD risk variables.

D.4. Sample Size and Power Considerations

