The second aim, which will examine within-person associations of changes in sleep efficiency with concomitant changes in cardiovascular indices, will have an ESS that is roughly equivalent to the total number of observations. With 150 participants contributing up to 2 change scores each, even with 10% attrition at each time point, the ESS is projected to be 256, which would have 80% power to detect an association equivalent to $\beta = .15$. A number of studies have established cross-sectional associations of sleep disturbance with cardiovascular risk factors (Spiegelhalder, Scholtes, & Riemann, 2010). In our own research, we have found that self-reported sleep disturbance is modestly associated with reduced heart-rate variability ($\beta = -.18$) and dyslipidemia (equivalent $\beta = .11$). We anticipate that these associations will be stronger in the proposed within-subjects analysis given the absence of random effects from between-person differences. Thus, the current trial should be sufficiently powered to detect even modest associations between concurrent changes in sleep efficiency and CVD risk parameters.

D.5. Data Sharing with Key Personnel Outside Duke

[name], at University of North Carolina at Chapel Hill, will perform some of the above-described statistical analyses in accordance with a sub-award to him. De-identified data will be shared with [name] via Box@Duke. No PHI, including dates, will be shared with [name].

E. STUDY TIMELINE

The overall data collection and analysis timeline is outlined in Table 3. Recruitment will occur in years 1 through 5. Intervention delivery and follow-ups will occur in years 1-5.

Table 3. Project Timeline

ACTIVITY	Year 1	Year 2	Year 3	Year 4	Year 5	Totals
Hiring/Training/Development	X					
Screening	26	48	47	47	31	199
Recruitment	20	35	35	35	25	150
DATA COLLECTION						
CVD & Sleep Measures	20	35	35	35	25	150
Treatment Waitlist	20	35	35	35	25	150
Post Assessment	15	38	34	32	23	142
6-month Assessment	0	40	38	41	23	142
Data Processing				X	X	
Data Analysis					X	

References

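### The Hypothesis 2 power figure in D.4 does not follow from its inputs: 256 change scores give about 67% power at β = .15 with a two-sided test at .05, not 80%

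*Combined protocol and SAP*

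**What the plan says.** The Aim 2 paragraph of D.4 (Sample Size and Power Considerations) starts from "With 150 participants contributing up to 2 change scores each" and, "even with 10% attrition at each time point", arrives at an effective sample size (ESS) of 256. It equates the ESS with the number of change scores. It then says that "the ESS is projected to be 256, which would have 80% power to detect an association equivalent to" β = .15. It gives no alpha, sidedness or covariate contribution.

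The only test convention in D.4 is in the Hypothesis 1 paragraph just before, where d = 0.41 is said to be detectable with 80% power "via a two-tailed test with an alpha of .05".

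D.3 specifies the Hypothesis 2 model. Change in the biomarker is modelled "as a function of corresponding change in sleep efficiency, covarying for sleep efficiency measured at" the previous visit, and also for the biomarker's own previous value. D.1 adds that a false discovery rate correction will apply to Aims 1 and 2.

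D.4 cites the team's own cross-sectional associations of −.18 and .11 and says: "We anticipate that these associations will be stronger in the proposed within-subjects analysis given the absence of random effects from between-person differences". It concludes: "Thus, the current trial should be sufficiently powered to detect even modest associations between concurrent changes in sleep efficiency and CVD risk parameters".

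**The concern.** The two paragraphs of D.4 appear to use different conventions. A reader carries the two-tailed .05 test forward from Hypothesis 1, because nothing replaces it, and on that basis the Aim 2 figure is about 12 to 13 percentage points too high.

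The statement of adequate power for modest associations rests on this figure. If Aim 2 finds no association, the result will be read against a claimed 80% power at β = .15. If the true power is nearer two in three, a missed association could be taken as evidence that sleep efficiency and cardiovascular risk do not change together.

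**Working it through.** **Inputs.** From D.4: 150 participants, up to 2 change scores each, 10% attrition at each time point, ESS 256, β = .15, power 80%, and (from the Hypothesis 1 paragraph) two-tailed alpha .05. From Table 3: 142 post-intervention and 142 six-month assessments. β is read as a standardized coefficient.

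**1. The ESS reproduces.** 150 × .90 + 150 × .90² = 135 + 121.5 = 256.5.

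**2. The two-tailed convention reproduces Hypothesis 1.** An ESS of 215 split 2:1 gives groups of 143.3 and 71.7. The noncentrality is 0.41 / √(1/71.7 + 1/143.3) = 2.83. Power by noncentral t is 80.5% two-tailed and 88.1% one-tailed. The stated 80% is therefore a two-tailed figure.

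**3. The same convention applied to Hypothesis 2.** By Fisher z, power = Φ(atanh(β) × √(n − 3) − 1.960). With β = .15 and n = 256:

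atanh(.15) × √253 = .1511 × 15.906 = 2.404, and Φ(2.404 − 1.960) = Φ(0.444) = 67.2%.

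The noncentral t for a regression slope, with f² = β²/(1 − β²), gives 67.7%, and still 67.7% with three predictors as in the D.3 model. Rounding does not explain the gap: β = .155 gives at most 70.6%.

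**4. Other counts of change scores, two-sided .05.**

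| Change scores | Source | Power at .15 (Fisher z / t) | β detectable at 80% (t / Fisher z) |
|---|---|---|---|
| 256 | D.4 attrition | 67.2% / 67.7% | .173 / .174 |
| 284 | Table 3, 142 + 142 | 71.7% / 72.2% | .165 / .166 |
| 300 | no attrition | 74.1% / 74.5% | .160 / .161 |

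For 80% power at .15 the number required is ((1.960 + 0.842)/.1511)² + 3 ≈ 347 by Fisher z, or 343 by noncentral t. Both exceed the maximum of 300.

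**5. One-sided .05, n = 256.** Power at .15 is 77.6% (Fisher z) or 78.1% (t). The detectable β is .154 by t.

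**6. Effect of the lagged covariates.** Let r_SE and r_B be the visit-to-visit correlations of sleep efficiency and of the biomarker, with equal variances at each visit. Adjusting for the previous value leaves a fraction (1 + r)/2 of the variance of each change score. The information on the slope is then multiplied by (1 + r_SE)/(1 + r_B). The plan gives no such correlations for Hypothesis 2, so the values below are assumptions.

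| r_SE / r_B (assumed) | Factor | Power at .15, two-sided .05, n = 256 |
|---|---|---|
| .5 / .8 | 0.83 | 60% |
| .5 / .5 | 1.00 | 68% |
| .8 / .5 | 1.20 | 76% |
| .8 / .35 | 1.33 | 80% |

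Reaching 80% needs a factor of about 343/256 = 1.34. That corresponds to covariates removing about 25% of the outcome-change variance with no loss of variance in the predictor.

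**7. The plan's own benchmarks, two-sided .05, n = 256 (t).** An association of .18 has 83% power, and one of .11 has 42%.

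**The case against.** The strongest reply is that the two-tailed convention is imported. It closes a sentence about Cohen's d for Hypothesis 1, while Hypothesis 2 is worded directionally. A one-sided test at .05 has a detectable β of .154, which rounds to .15.

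A second route uses the intra-individual correlation of .50 that D.4 gives for Hypothesis 1. With equal variances, the lagged outcome would then explain (1 − .5)/2 = 25% of outcome-change variance. If β² is read as a unique share of variance, two-sided power at n = 256 is 80.0%. On this view the plan has a reporting gap, not an arithmetic error. The practical effect is also small: the detectable β moves from .15 to .173, and the cited .18 keeps 83% power.

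Part of this stands. Either route may be where the figure came from, the .18 benchmark is adequately powered, and the plan expects within-person associations to be stronger than the cross-sectional ones.

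The main point is not met. No one-sided test is declared anywhere, and D.4's Hypothesis 1 figure is demonstrably two-tailed. The 25% route borrows a correlation stated only for Hypothesis 1 and applies it to the outcome alone. Applying the same .50 to sleep efficiency, which D.3 also adjusts for at the previous visit, makes the factor 1.5/1.5 = 1 and returns power to 67.7%.

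**Conclusion.** The concern holds. Under the only convention D.4 states, power for Hypothesis 2 at β = .15 is 67–68%, not 80%, and the association detectable with 80% power is about .173.

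This rests on a two-sided test at .05, 256 change scores treated as independent (as D.4 treats them), β as a standardized coefficient, and no net gain or loss from the lagged covariates. The false discovery rate correction is not applied in this calculation, and it can only reduce power. The finding does not show that .15 is unattainable under every set of assumptions. It shows that the figure does not follow from what the plan states. The sample size and the analysis model are unaffected.

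**What to change.** Revise the Aim 2 paragraph of D.4 in one of two ways:

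- State that 256 change scores give 80% power for β of about .17 (two-sided alpha .05, before the false discovery rate correction, no net gain from the lagged covariates), and that power at β = .15 is about 67%.
- Or keep .15, and state the alpha, the sidedness, the meaning of β and the covariate assumptions that produce it.

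In either case, qualify the closing sentence on modest associations. An association as small as the cited .11 would have about 42% power if the within-person effect is no stronger than that; the plan expects it to be stronger, and the text should say that this is an expectation.

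The cost is a change of SAP wording and a slightly less favourable stated figure. No extra participants or design changes are needed.
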